3.6 Visit Impact of Logistical Restriction Due to COVID-19

Visit impact of logistical restriction due to the COVID-19 pandemic will be summarized by the type of impact (missed visit, in person/partial assessment done, and virtual visit/phone call) recorded on the Visit Impact CRF page for each treatment arm.

Information for treatment discontinuation and study exit during the COVID-19 pandemic will be listed.

Analyses or summaries for efficacy and safety data related to COVID-19 are described in Section 4.1 and Section 5.1, respectively.

Page 20 of 35

4 ANALYSIS FOR EFFICACY ENDPOINTS

Analyses of efficacy endpoints will be conducted using the ITT population, unless otherwise specified. For subgroup, sensitivity, and exploratory analyses, only the analyses that provide meaningful information will be presented in the CSR.

There are three randomization stratification factors as recorded in IRT: prior lines of therapy $(1-2 \text{ vs} \ge 3)$, ECOG performance status (0-1 vs 2), and TLS risk category (low risk vs. increased risk). Since only 9 subjects in total were randomized to the stratum of ECOG performance status of 2, stratification by those three factors will result in empty or very small strata. Therefore, all stratified tests/analyses will only be based on two randomization stratification factors per IRT: prior lines of therapy $(1-2 \text{ vs} \ge 3)$ and TLS risk category (low risk vs. increased risk).

The investigators will perform the overall disease assessment based on the Revised Response Criteria for Malignant Lymphoma (Cheson 2014, Lugano Classification³); referred to as Cheson 2014 or Lugano Classification Criteria. An Independent Review Committee (IRC) will be implemented to conduct the overall disease assessments based on the same criteria.

The overall disease assessment per the investigators will be used to conduct the primary efficacy analyses, and the overall disease assessment per IRC will be used to conduct sensitivity analyses.

Due to differences in the preferred censoring approach for PFS across jurisdictions, the estimand and analyses for PFS will be described separately for the US and other regions (see Section 4.1 and Section 4.2).

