1 BACKGROUND

1.1 Mantle Cell Lymphoma

1.1.1 Disease Background

Mantle cell lymphoma (MCL) is a distinct clinical-pathologic entity within the non-Hodgkin's lymphomas (NHL). Initially termed "centrocytic lymphoma" in the Kiel Classification system (Lennert 1981), MCL has subsequently been shown to harbor the translocation t(11,14)(q13;q32), which results in constitutive overexpression of cyclin D1 (Zucca 1994). These features are now considered requisite for the diagnosis of the disease.

Mantle cell lymphoma accounts for about 6-9% of all NHL cases in the Western world. The annual incidence of MCL has increased during recent decades to 1-2/100,000. MCL occurs more frequently in older adults (Zhou 2008). Most patients with MCL are men (median age: 65 years) who present with advanced stage disease (ie, Stage III or IV) and most cases follow an aggressive clinical course (Dreyling 2014). The typical presentation is with generalized lymphadenopathy, and extranodal involvement frequently occurs in the gastrointestinal tract, spleen, bone marrow, and liver; less common extranodal sites are skin, lungs, and breast or soft tissues. Though the clinical course of MCL may be somewhat indolent at diagnosis, the course invariably becomes aggressive over time. Unlike other NHLs, MCL is considered incurable with standard therapies and is associated with a poor prognosis and a relatively short median overall survival (OS) (Lenz 2004). There is no curative therapy for MCL. A few patients may achieve long-term, disease-free survival after allogeneic stem cell transplantation (Goy 2011), but in general, the disease is characterized by a series of relapses with a median OS of 4 to 5 years. A number of MCL prognostic variables have been identified, including the presence or absence of extranodal disease, age, lactate dehydrogenase (LDH) levels, performance status, and Ki-67 proliferative index (Hoster 2008).

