2.2 Definition of Subgroups

Analyses for the baseline subgroups will be performed for selected variables. The baseline subgroup variables (Table 1) and the cutoff values are subject to change (if warranted) to better represent the data,

 Table 1
 Baseline Subgroups

Baseline Subgroup	Definition of Baseline Subgroup	Analysis Type
Age	< 65, ≥ 65	E, S
Gender	Male, Female	E, S
Race	White, Non-White	E, S
Geographic region	North America, Europe, Asia Pacific	B, E, S
Number of prior lines of therapy (1-2 vs. ≥3) per CRF	1-2, ≥ 3	Е
ECOG performance status per CRF	0, 1-2	Е
TLS risk category per CRF	Low Risk, Increased Risk	Е
Simplified MIPI score	Low Risk, Intermediate Risk, High Risk	Е
Bulky tumor (largest long diameter) per investigator	< 5 cm, ≥ 5 cm	Е
Enlargement of spleen per investigator	Yes, No	Е
Extranodal disease per investigator	Presence, Absence	Е

Page 16 of 35

Baseline Subgroup	Definition of Baseline Subgroup	Analysis Type
Blastoid variant and/or pleomorphic variant of MCL	Yes, No	Е
Blastoid variant of MCL	Yes, No	Е
TP53 Mutation	Mutated, Not Mutated, Not Performed/Missing	Е
Prior stem cell transplant (SCT)	Yes, No	Е
Renal function (creatinine clearance)	< 60 mL/min, ≥ 60 mL/min	S
Hepatic function (NCI ODWG definition)	normal, mild, moderate, severe (or normal vs. abnormal as appropriate)	S

Analysis type: B=Subject Demographics, Baseline Characteristics, Baseline Disease Characteristics; E = Efficacy (PFS); MIPI: MCL International Prognostic Index; MRD: Minimal Residual Disease; NCI ODWG: NCI Organ Dysfunction Working Group Liver Function Classification (Ramanathan et al, 2008); S = Safety (Overview TEAE, TEAE by SOC/PT, Grade 3 or higher TEAE by SOC/PT).

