4.2 Definitions and Analyses for Efficacy Endpoints

Table 2 below describes the definitions and analyses for the efficacy endpoints.

 Table 2
 Definitions and Analyses for Efficacy Endpoints

Efficacy Endpoint	Definition	Analysis Method			
	Primary Endpoint				
PFS assessed by investigator (INV)	Time from the date of randomization to the date of the first documentation of progressive disease (PD) or the date of death due to any causes, whichever occurs first, regardless of study drug discontinuation or use of subsequent anti-cancer treatment. Post-treatment stem cell transplantation, CAR T-cell therapy, and other cellular therapies are not considered subsequent anti-cancer treatment for subjects responding to treatment (CR or PR) For the evaluation of disease progression, an adequate post-baseline assessment is defined as an assessment where there is enough evidence to indicate the subject had or had not progressed based on Cheson 2014 (Lugano Classification Criteria). In the situation where subjects did not have a baseline disease assessment or any adequate post-baseline disease assessment, they will be censored at the date of randomization.	Primary Analysis: Treatment policy strategy and composite variable strategy as listed in Section 4.1 will be implemented to address intercurrent events. Subjects without a PFS event will be censored at the date of the last adequate post-baseline disease assessment showing no evidence of disease progression. For US, additional censoring conventions will be implemented [see Sensitivity/Supplementary Analyses item 3) below]. Stratified log-rank test will be used to test the treatment effect between the two treatment arms. Stratified Cox regression model with Efron's tie handling method will be used to calculate the hazard ratio (HR) and its 2-sided 95% confidence interval (CI). In addition, Kaplan-Meier (KM) curves will be provided for both treatment arms. For each treatment arm, the 2-sided 95% Brookmeyer-Crowley confidence interval based on the log-log-transformed Greenwood variance estimate will be calculated for median PFS (mPFS); KM estimates at selected landmark points will also be provided.			

Page 23 of 35

Sensitivity/Supplementary Analyses:

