	To support ORR, duration of response (DOR) is defined for the responders (PR or CR) as time from the date of initial response (PR or CR, whichever occurs first) to the date of first documentation of PD or death, whichever occurs first, regardless of the use of subsequent anticancer therapy. Censoring convention is the same as for the PFS primary analysis.	
	For the US, additional censoring conventions as specified for the US primary PFS analysis in item 3) under Analysis Method will be implemented for duration of response.	
Minimal Residual Disease (MRD)- Negative Remission Rate	For CR subjects per investigator only: Proportion of subjects achieving an MRD- negative remission, which is defined as undetectable MRD (i.e. less than the lower limit of detection for the assay) at documented CR in MRD-evaluable subjects (i.e. subjects with positive MRD at baseline) as assessed by flow cytometry of bone marrow aspirate (BMA) and/or peripheral blood (PB)), with requirement of a confirmation of MRD- negativity in subsequent peripheral blood samples at least 12 weeks later. Only subjects with samples collected at both baseline and post-baseline are included in the	For CR subjects who were MRD-evaluable, the MRD-negative remission rate will be calculated and tested by Fisher's Exact test for BMA and PB separately.
	baseline and post-baseline are included in the denominator when calculating the MRD remission rate. MRD samples collected after the initiation of subsequent anticancer therapy will not be used for this analysis.	

Efficacy Endpoint	Definition	Analysis Method	
Overall	Time from the date of randomization to the	Primary Analysis:	
Survival (OS)	date of death due to any cause.	Similar to the primary PFS analysis, composite variable strategy (COVID-19 deaths are considered OS events) is implemented to address the intercurrent events of COVID-19 deaths. Subjects without an OS event will be censored at the date last known alive.	
		Analysis methods are the same as the primary PFS analysis.	
		Sensitivity/ Supplemental Analyses:	
		1) Unstratified log-rank test and unstratified Cox regression model to calculate HR and its 2-sided 95% CI.	
		2) Hypothetical strategy (Subjects who died due to COVID-19 are censored at one day prior to the death date) is implemented to address the intercurrent events of COVID-19 deaths	

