Time to next treatment (TTNT)	Time from the date of randomization to the date of the initiation of subsequent anti-cancer treatment. Post-treatment stem cell transplantation, CAR T-cell therapy, or other cellular therapies are not considered subsequent anti-cancer treatments for subjects responding to the treatment (CR or PR). Subjects without the use of subsequent anti-cancer treatment will be censored at the last follow-up date for subsequent anti-cancer therapy.	Method is the same as for the PFS analysis	
Time to worsening in FACT- Lym subscale ^{5,6}	Time from the date of randomization to the start date of worsening (defined by a ≥5 points reduction from baseline) in the Lym Subscale or death due to any cause, whichever occurs first.	Method is the same as for the PFS analysis	
	Subjects who have not met the definition of worsening will be censored at the last non-missing post-baseline PRO assessment. Subjects without baseline or post-baseline assessment will be censored at the date of randomization.		

Page 27 of 35

Efficacy Endpoint	Definition	Analysis Method			
	Exploratory Endpoints				
Progression- free Survival Based on Investigator Assessment after Initiation of Subsequent Anti-cancer Therapy (PFS2)	Time from the date of randomization to the date of the earliest of the following three types of events: • PD per investigator response assessment after administration of the first subsequent anticancer therapy • Death at any time on study • Initiation of the second subsequent anticancer therapy Subjects who did not experience a PFS2 event will be censored at the last adequate response assessment or the last follow-up for subsequent anti-cancer therapy (if they no longer have response assessments).	No inferential test will be conducted. For each treatment arm, the KM estimate of the median PFS2 (mPFS2) and the KM estimates at selected landmark points will be calculated using the same methods as for the primary PFS analysis.			

CMH: Cochran-Mantel-Haenszel; CI: confidence interval; CR: complete response; HR: estimate hazard ratio; ORR: overall response rate; OS: overall survival; PD: progressive disease; PFS: progression-free survival; PR: partial response.

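### No efficacy analysis adjusts for simplified MIPI or baseline Lym score, so a chance imbalance on either would stay uncorrected in the reported hazard ratio

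*SAP*

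**What the plan says.** SAP section 4 drops ECOG from the three randomization factors, giving the reason: "Since only 9 subjects in total were randomized to the stratum of ECOG performance status of 2". From then on, "all stratified tests/analyses will only be based on two randomization stratification factors per IRT": prior lines (1-2 vs ≥3) and TLS risk (low vs increased).

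SAP Table 2 (section 4.2) carries this through the time-to-event endpoints:
- PFS: "Stratified log-rank test will be used to test the treatment effect between the two treatment arms", with a stratified Cox model for the hazard ratio.
- OS: "Analysis methods are the same as the primary PFS analysis".
- TTNT and time to worsening in the FACT-Lym subscale: "Method is the same as for the PFS analysis". Worsening is "defined by a ≥5 points reduction from baseline" in the Lym subscale, or death.

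The PFS sensitivity and supplementary analyses vary the censoring, the assessor, the handling of COVID-19 deaths, and stratified against unstratified. Those for OS cover only an unstratified version and COVID-19 deaths. No analysis adds a covariate.

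The baseline information is nevertheless there. Protocol 1.1.1 states: "A number of MCL prognostic variables have been identified, including the presence or absence of extranodal disease, age, lactate dehydrogenase (LDH) levels, performance status". SAP 2.2 lists "Simplified MIPI score" in three levels, but only as a PFS subgroup, and SAP section 2 plans no tests for subgroups. Protocol 7.1.5.1 collects FACT-Lym on Week 1 Day 1.

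**The concern.** With ECOG gone, none of the variables that the protocol names as prognostic enters an efficacy model; they appear only in baseline tables and PFS subgroups. The one planned variation in adjustment, the unstratified analysis, removes factors and adds none.

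In a trial of 260 subjects the arms can differ on MIPI by chance. If they do, the reported hazard ratio carries that difference, in either direction, and the SAP names no analysis that would show how much of the result it explains. A MIPI-adjusted model first fitted after unblinding would look selected. SAP section 4 sharpens this, because it allows the study report to show only those sensitivity analyses judged informative.

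FACT-Lym worsening has a second link to baseline. The event is a fall from the subject's own starting score, so its probability depends on that score. The Lym subscale runs from 0 to 60, and a subject who starts below 5 cannot fall by 5 points and can have an event only by dying.

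**Working it through.** **1. The plan's own figure.** Inputs from SAP 1.4.1: HR 0.61, one-sided 0.025, about 80% power, 1:1. Freedman's formula gives (1.960 + 0.842)² × (1.61/0.39)² = 7.85 × 17.04 = 134 events, as stated. Schoenfeld power is 81.6% at 134 events and 85.7% at the 150 events of SAP 1.5.1.

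**2. How likely is an imbalance?** With 130 per arm and an assumed share p of MIPI-high subjects, the SD of the between-arm difference is √(2p(1−p)/130), treating allocation as simple randomization.

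| p | SD (points) | P(difference over 10 points) |
|---|---|---|
| 0.30 | 5.7 | 7.9% |
| 0.40 | 6.1 | 10.0% |
| 0.50 | 6.2 | 10.7% |

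**3. What would it do to the hazard ratio?** Let g be the hazard ratio per MIPI step, and k the number of steps between the surplus high-risk subjects and those they displace (1 if intermediate, 2 if low). To first order, a 10-point imbalance multiplies the unadjusted HR by g^(0.10k).
- g = 1.0: no shift.
- g = 1.5: 1.5^0.10 = 1.041 to 1.5^0.20 = 1.084.
- g = 2.0: 2.0^0.10 = 1.072 to 2.0^0.20 = 1.149.

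Simulation gave about 5% at g = 1.5 and 13% at g = 2.0, inside these brackets, and about 0 to 2% once MIPI was in the model. Applied to the design HR, 0.61 × 1.05 = 0.64 and 0.61 × 1.13 = 0.69. In the favourable direction, 0.61/1.05 = 0.58 and 0.61/1.13 = 0.54. With a standard error of log HR of about 0.167 at 150 events, the shifts are ln 1.05/0.167 = 0.3 and ln 1.13/0.167 = 0.7 standard errors.

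**4. What adjustment does not do.** Simulated trials used 260 subjects, four strata, 21-month accrual and assumed MIPI shares of 25/35/40%. At 134 PFS events the standard error was 0.177 for the SAP's analysis and 0.178 to 0.179 with MIPI as a covariate. One-sided type I error at g = 2.0 was 2.7% and 2.6%.

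Power below applies only if the MIPI-adjusted test replaced the SAP's test, with the design HR taken as the within-MIPI HR:

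| g | PFS, 134 events: SAP / adjusted | PFS, 150 events | OS, 170 events |
|---|---|---|---|
| 1.0 | 79.8 / 79.1% | 85.4 / 85.3% | 79.3 / 78.6% |
| 1.3 | 79.1 / 80.7% | 83.2 / 83.8% | not run |
| 1.5 | 77.0 / 78.9% | 82.9 / 85.4% | 75.8 / 77.8% |
| 2.0 | 71.6 / 78.9% | 75.1 / 83.5% | 68.7 / 77.8% |

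**5. Covariate or extra strata?** Adding MIPI as strata gives 4 × 3 = 12 cells. At 134 events the standard error rises to 0.183. Power is 76.4% at g = 1.0, a loss of 3.4 points against the SAP's analysis, and 76.9% at g = 1.5.

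**6. FACT-Lym.** The documents give no SD or correlation. Assume SD 9 at each visit, correlation ρ of 0.5 to 0.7 with baseline, and no mean change. For a subject z SDs from the baseline mean, the chance of a fall of at least 5 at one visit is Φ[(−5 + 9(1−ρ)z)/(9√(1−ρ²))].
- ρ = 0.5: z = −1 gives Φ(−9.5/7.79) = 11%; z = +1 gives Φ(−0.5/7.79) = 47%.
- ρ = 0.7: z = −1 gives Φ(−7.7/6.43) = 12%; z = +1 gives Φ(−2.3/6.43) = 36%.

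Under the same SD and correlations, a simulation of the worsening event gave about 29 to 30% in the lowest third of baseline scores and 74 to 85% in the highest.

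**The case against.** The case against is strong on several counts, and most of it stands.

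- **Precision.** A reader might infer that leaving MIPI out makes the estimate less precise. It does not: in a Cox model the standard error of the log HR is practically unchanged.
- **Attenuation and lost power.** A reader might infer that the planned HR is biased towards 1 and that power is being lost. SAP 4.1 defines the summary as the hazard ratio between the two arms. A MIPI-conditional HR is a different quantity. The 0.61 comes from overall medians of 14 and 23 months, so treating it as the within-MIPI value weakens the overall HR by construction. The power differences in step 4 also run from about −1 to +9 points on an assumed effect, and none would be realised while the log-rank test stays primary.
- **Validity.** Randomization protects the planned test, and chance imbalance is already part of its unconditional error. Dropping ECOG is justified by the 9 subjects and disclosed in SAP section 7.
- **Existing safeguards.** Baseline characteristics are tabulated by arm, and PFS hazard ratios are shown within each MIPI level. This helps, but it gives no single adjusted estimate and does not cover OS.
- **FACT-Lym.** The endpoint is outside the alpha hierarchy of SAP 1.6.1, and no gain can be derived from the documents. The dependence on baseline, however, follows from the event definition itself.

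**Conclusion.** The point holds as a missed robustness step. It is an inexpensive improvement; the planned analysis contains no error here. The documents establish that no covariate-adjusted analysis is planned while the covariates are available, and that FACT-Lym worsening is defined against a baseline score that is not in its model.

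The size is not established by the documents, which give neither a MIPI hazard ratio nor a MIPI distribution. For an assumed 1.5 to 2.0 per step, a 10-point imbalance shifts the unadjusted HR by about 5 to 13%. An imbalance above 10 points has a probability of about 8 to 11%, for an assumed 30 to 50% MIPI-high. If MIPI is not prognostic, there is no gain. The FACT-Lym figures rest wholly on an assumed SD and correlation. The documents do not support any claim of an invalid test, a biased primary HR or an underpowered primary analysis.

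**What to change.** Before unblinding, amend the SAP as follows.

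1. Keep the two-factor stratified log-rank test and its stratified HR as primary for PFS and OS.
2. Add to the PFS and OS sensitivity analyses a Cox model with the same two strata plus simplified MIPI (3 levels) as a covariate, not as extra strata. Label the result a conditional HR, not directly interchangeable with the primary one.
3. State a rule for missing MIPI, for example a missing category.
4. Include the continuous baseline Lym score as a covariate in the Cox model for time to worsening in FACT-Lym.

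The cost is a few lines of SAP text and two or three model fits on data already planned. The primary test, its type I error and its power are untouched. The small downside is that a second HR with a conditional interpretation is reported beside the primary one and has to be explained.

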anticancer therapy	strategy Supplementary analysis: treatment	strategy Supplementary analysis:
	policy strategy	hypothetical strategy
Death due to COVID-19	Primary analysis: composite variable strategy	
	Supplementary analysis: hypothetical strategy	

4.2 Definitions and Analyses for Efficacy Endpoints

Table 2 below describes the definitions and analyses for the efficacy endpoints.

 Table 2
 Definitions and Analyses for Efficacy Endpoints

Efficacy Endpoint	Definition	Analysis Method			
	Primary Endpoint				
PFS assessed by investigator (INV)	Time from the date of randomization to the date of the first documentation of progressive disease (PD) or the date of death due to any causes, whichever occurs first, regardless of study drug discontinuation or use of subsequent anti-cancer treatment. Post-treatment stem cell transplantation, CAR T-cell therapy, and other cellular therapies are not considered subsequent anti-cancer treatment for subjects responding to treatment (CR or PR) For the evaluation of disease progression, an adequate post-baseline assessment is defined as an assessment where there is enough evidence to indicate the subject had or had not progressed based on Cheson 2014 (Lugano Classification Criteria). In the situation where subjects did not have a baseline disease assessment or any adequate post-baseline disease assessment, they will be censored at the date of randomization.	Primary Analysis: Treatment policy strategy and composite variable strategy as listed in Section 4.1 will be implemented to address intercurrent events. Subjects without a PFS event will be censored at the date of the last adequate post-baseline disease assessment showing no evidence of disease progression. For US, additional censoring conventions will be implemented [see Sensitivity/Supplementary Analyses item 3) below]. Stratified log-rank test will be used to test the treatment effect between the two treatment arms. Stratified Cox regression model with Efron's tie handling method will be used to calculate the hazard ratio (HR) and its 2-sided 95% confidence interval (CI). In addition, Kaplan-Meier (KM) curves will be provided for both treatment arms. For each treatment arm, the 2-sided 95% Brookmeyer-Crowley confidence interval based on the log-log-transformed Greenwood variance estimate will be calculated for median PFS (mPFS); KM estimates at selected landmark points will also be provided.			

Page 23 of 35

Sensitivity/Supplementary Analyses:
1) To address the intercurrent events of use of subsequent anticancer therapy, hypothetical strategy (subjects who received subsequent anti-cancer treatment will be censored at the last adequate post-baseline disease assessment showing no evidence of PD prior to the initiation of subsequent anti-cancer treatment) is implemented.
2) Subjects who missed two or more consecutive overall disease assessments (algorithm is described in Appendix 1) prior to the PFS event will be censored at the last adequate post-baseline disease assessment showing no evidence of PD prior to the first missed disease assessment.
3) Implement the two censoring conventions from items 1) and 2) above. This will be the primary analysis only for the US regulatory consideration.
4) Analyses listed under Primary Analysis and Sensitivity/Supplementary Analyses items 1) - 3) will be repeated for the IRC assessment.
5) To address the intercurrent events of COVID-19 deaths, hypothetical strategy (Pre-PD deaths due to COVID-19 are censored) is implemented.
6) Unstratified log-rank test and unstratified Cox regression model to calculate HR and its 2-sided 95% CI; same censoring convention as the primary analysis.
Subgroup Analysis: Hazard ratio and its 95% CI from unstratified Cox regression model for each subgroup. Same censoring convention as for the primary analysis.
For the US, additional censoring conventions as specified for the US primary PFS analysis in item 3) above will be implemented.

Efficacy Endpoint	Definition	Analysis Method			
Secondary Endpoints					
CR Rate per INV	Proportion of subjects achieving a complete response (CR) based on the best overall response (BOR) per Cheson 2014 (Lugano Classification Criteria) recorded since the date of randomization until the initiation of subsequent anti-cancer treatment or the first documentation of progressive disease, whichever occurs first. Subjects who did not have any post-baseline disease assessments will be considered non-responders when summarizing CR rate. For responding subjects who received post-treatment stem cell transplantation (SCT), CAR T-cell therapy, or other cellular therapies, BOR will be based on disease assessments conducted prior to these treatments. To support CR rate, duration of CR is defined as time from the date of first documentation of CR to the date of first documentation of PD or death, whichever occurs first, regardless of the use of subsequent anti-cancer treatment. Censoring convention is the same as for the PFS primary analysis. For the US, additional censoring conventions as specified for the US primary PFS analysis in item 3) under Analysis Method will be	Primary Analysis: Rate ratio between the two treatment arms will be calculated and tested using the Cochran-Mantel-Haenszel (CMH) chi-square test stratified by the two randomization stratification factors. Supportive Analysis For duration of CR, the KM estimate of median and the KM estimates at selected landmark points will be provided for each treatment arm.			
ORR per INV	implemented for duration of CR. Proportion of subjects achieving a complete response (CR) or partial response (PR) based on the best overall response (BOR) per Cheson 2014 (Lugano Classification Criteria) recorded since the date of randomization until the initiation of subsequent anti-cancer treatment or the first documentation of progressive disease, whichever occurs first. Subjects who	Primary Analysis: Method is the same as for the CR rate. Supportive Analysis: Same KM estimates described above for duration of CR will be provided for DOR.			

Efficacy Endpoint	Definition	Analysis Method
_	did not have any post-baseline disease assessments will be considered non-responders when summarizing ORR.	
	To support ORR, duration of response (DOR) is defined for the responders (PR or CR) as time from the date of initial response (PR or CR, whichever occurs first) to the date of first documentation of PD or death, whichever occurs first, regardless of the use of subsequent anticancer therapy. Censoring convention is the same as for the PFS primary analysis.	
	For the US, additional censoring conventions as specified for the US primary PFS analysis in item 3) under Analysis Method will be implemented for duration of response.	
Minimal Residual Disease (MRD)- Negative Remission Rate	For CR subjects per investigator only: Proportion of subjects achieving an MRD- negative remission, which is defined as undetectable MRD (i.e. less than the lower limit of detection for the assay) at documented CR in MRD-evaluable subjects (i.e. subjects with positive MRD at baseline) as assessed by flow cytometry of bone marrow aspirate (BMA) and/or peripheral blood (PB)), with requirement of a confirmation of MRD- negativity in subsequent peripheral blood samples at least 12 weeks later. Only subjects with samples collected at both baseline and post-baseline are included in the	For CR subjects who were MRD-evaluable, the MRD-negative remission rate will be calculated and tested by Fisher's Exact test for BMA and PB separately.
	baseline and post-baseline are included in the denominator when calculating the MRD remission rate. MRD samples collected after the initiation of subsequent anticancer therapy will not be used for this analysis.	

Efficacy Endpoint	Definition	Analysis Method	
Overall	Time from the date of randomization to the	Primary Analysis:	
Survival (OS)	date of death due to any cause.	Similar to the primary PFS analysis, composite variable strategy (COVID-19 deaths are considered OS events) is implemented to address the intercurrent events of COVID-19 deaths. Subjects without an OS event will be censored at the date last known alive.	
		Analysis methods are the same as the primary PFS analysis.	
		Sensitivity/ Supplemental Analyses:	
		1) Unstratified log-rank test and unstratified Cox regression model to calculate HR and its 2-sided 95% CI.	
		2) Hypothetical strategy (Subjects who died due to COVID-19 are censored at one day prior to the death date) is implemented to address the intercurrent events of COVID-19 deaths	
Time to next treatment (TTNT)	Time from the date of randomization to the date of the initiation of subsequent anti-cancer treatment. Post-treatment stem cell transplantation, CAR T-cell therapy, or other cellular therapies are not considered subsequent anti-cancer treatments for subjects responding to the treatment (CR or PR). Subjects without the use of subsequent anti-cancer treatment will be censored at the last follow-up date for subsequent anti-cancer therapy.	Method is the same as for the PFS analysis	
Time to worsening in FACT- Lym subscale ^{5,6}	Time from the date of randomization to the start date of worsening (defined by a ≥5 points reduction from baseline) in the Lym Subscale or death due to any cause, whichever occurs first.	Method is the same as for the PFS analysis	
	Subjects who have not met the definition of worsening will be censored at the last non-missing post-baseline PRO assessment. Subjects without baseline or post-baseline assessment will be censored at the date of randomization.		

Page 27 of 35

Efficacy Endpoint	Definition	Analysis Method			
	Exploratory Endpoints				
Progression- free Survival Based on Investigator Assessment after Initiation of Subsequent Anti-cancer Therapy (PFS2)	Time from the date of randomization to the date of the earliest of the following three types of events: • PD per investigator response assessment after administration of the first subsequent anticancer therapy • Death at any time on study • Initiation of the second subsequent anticancer therapy Subjects who did not experience a PFS2 event will be censored at the last adequate response assessment or the last follow-up for subsequent anti-cancer therapy (if they no longer have response assessments).	No inferential test will be conducted. For each treatment arm, the KM estimate of the median PFS2 (mPFS2) and the KM estimates at selected landmark points will be calculated using the same methods as for the primary PFS analysis.			

CMH: Cochran-Mantel-Haenszel; CI: confidence interval; CR: complete response; HR: estimate hazard ratio; ORR: overall response rate; OS: overall survival; PD: progressive disease; PFS: progression-free survival; PR: partial response.

